7.2 INCLUSION CRITERIA

- I 01. Male or female patient aged >6 months old and <70 years old:
- Cohort 1 = 14 years $<$ age <70 years and body weight ≥ 35 kg,
 - Cohort 2 = 5 years $<$ age ≤ 14 years,
 - Cohort 3 = 2 years $<$ age ≤ 5 years,
 - Cohort 4 = 6 months $<$ age ≤ 2 years.
- I 02. Body weight ≥ 5 kg and ≤ 90 kg.
- I 03. Presence of mono-infection by *P. falciparum* with:
- a) Fever, as defined by axillary temperature $\geq 37.5^{\circ}\text{C}$ or oral/rectal/tympanic temperature $\geq 38^{\circ}\text{C}$, or history of fever in the previous 24 hours (history of fever must be documented) and,
 - b) Microscopically (blood smear) confirmed parasite infection, ranging from 1000 to 100 000 asexual parasites/ μL of blood.

- I 04. Informed Consent Form signed by the patient (if the patient is \geq age defining majority) or parent or by the legally acceptable representative of the minor patient (<18 years of age or < other age locally defining majority). In addition, in accordance with local regulation, minor participants with capacity for writing could sign off on an Assent Form. For those who are able to understand but with no capacity for writing the Assent Form would be read. In that case, an impartial witness could certify the document was read to the child.

7.3 EXCLUSION CRITERIA

Patients who have met all the inclusion criteria listed in [Section 7.2](#) will be screened for the following exclusion criteria which are sorted and numbered in the following three sub-sections:

7.3.1 Exclusion criteria related to study methodology

- E 01. Presence of severe malaria (according to WHO definition) (see [Appendix A](#)).
- E 02. Any anti-malarial treatment:
- With piperaquine -based compound, mefloquine, naphthoquine or sulphadoxine/pyrimethamine (SP) within the previous 6 weeks (after their inhibition of new infections has fallen below 50%).
 - With amodiaquine or chloroquine within the previous 4 weeks.
 - With quinine, halofantrine, lumefantrine-based compounds and any other anti-malarial treatment or antibiotics with antimalarial activity (including cotrimoxazole, tetracyclines, quinolones and fluoroquinolones, and azithromycin) within the past 14 days.
 - With any herbal products or traditional medicines, within the past 7 days.
- E 03. Known history or evidence of clinically significant disorders such as, respiratory (including active tuberculosis), hepatic, renal, gastrointestinal, immunological, neurological (including auditory), endocrine, infectious, malignancy, psychiatric, history of convulsions or other abnormality (including head trauma).
- E 04. Previous treatment within 5 times the half-life or within the last 14 days, whichever the longest which are: P-gp substrates, CYP2D6 main substrates and/or strong CYP2C or CYP3A inhibitors and/or moderate inhibitors but inhibiting both CYP2C and CYP3A and/or CYP inducers (see [Appendix B](#)).
- E 05. Mixed Plasmodium infection (ie, presence of another Plasmodium species in addition to *P. falciparum*).
- E 06. Severe vomiting, defined as more than three times in the 24 hours prior to enrollment in the study or inability to tolerate oral treatment, or severe diarrhea defined as 3 or more watery stools per day.
- E 07. Severe malnutrition (defined for patients aged ten years or less as the weight-for-height being below -3 standard deviation or less than 70% of median of the National Center for

Health Statistics/World Health Organization (NCHS/WHO) normalized reference values, and for patients aged greater than ten years, a body mass index (BMI) of less than 16 (11)

- E 08. Laboratory parameters with clinical significant abnormalities and/or reaching critical values. For Liver Function Test: aspartate transferase (AST) >2 ULN, or alanine transferase (ALT) >2 ULN or total bilirubin >1.5 ULN.
- E 09. Presence of Hepatitis A IgM (HAV-IgM), Hepatitis B surface antigen (HBsAg) or Hepatitis C antibody (HCV Ab).
- E 10. Have received an investigational drug within the past 4 weeks.
- E 11. Previous participation in any malaria vaccine study or received malaria vaccine in any other circumstance.
- E 12. Measles and yellow fever vaccine injection within the last 15 days or planned for the 28 days after randomization.
- E 13. Female patient of child bearing potential not willing to use an effective contraceptive(s) method(s) for the duration of the study (eg, implants, oral contraceptives, some intra-uterine devices or a double barrier method). The need for an efficient method will be reminded to the patient and the patient's legal guardian(s) by the investigator.
- E 14. Positive serum or urine beta-human chorionic gonadotropin (β -HCG) pregnancy test at study screening for female participants of childbearing potential.
- E 15. Breastfeeding women.
- E 16. Male patient having a partner of child bearing potential not willing to use an effective method of birth control for the duration of the study, or male patient wishing to father a child during study period.
- E 17. Splenectomized patients or presence of surgical scar on left hypochondrium.
- E 18. Patient unable to drink.

7.3.2 Exclusion criteria related to the current knowledge of Sanofi compound

- E 19. Known history of hypersensitivity, allergic or anaphylactoid reactions to ferroquine or other - aminoquinolines or to OZ439 or OZ277 or to any of the excipients.
- E 20. Family history of sudden death or of congenital prolongation of the QTc interval or known congenital prolongation of the QTc-interval or any clinical condition known to prolong the QTc interval eg, patients with a history of symptomatic cardiac arrhythmias or with clinically relevant bradycardia.
- E 21. QTcF >450 ms at screening or pre-dose.

E 22. Hypokalemia (<3.5 mmol/L), hypocalcemia (<2.0 mmol/L) or hypomagnesemia (<0.5 mmol/L) at screening or pre-dose.

E 23. Any treatment known to induce a lengthening of QT interval (see [Appendix C](#)).

7.4 PATIENT POPULATION

7.4.1 Patient sub-populations

7.4.1.1 Higher naturally acquired immunity population

Patients with higher probability of having developed NAI will be recruited (African patients >5 years old to <70 years old). Patients from this population will only be considered for DMC safety review.

- Cohort 1: African Patients >14 years and body weight ≥ 35 kg (for safety & PK/QTc evaluation only) *:
 - A minimum of 10 patients/arm (30 patients minimum if 3 treatment arms and 42 patients minimum if 4 treatment arms)
- Cohort 2: African Patients of >5 years and ≤ 14 years old (for safety evaluation only) *:
 - A minimum of 5 patients/arm (15 patients minimum if 3 treatment arms and 20 patients minimum if 4 treatment arms)

* If requested by DMC, additional patients may be included and evaluated for PK/QTc and/or safety.

7.4.1.2 Lower naturally acquired immunity population

This is the target population of interest. The study aims to recruit predominantly patients with lower probability of having developed NAI defined as:

- children >6 months to ≤ 5 years in Africa

Only patients from this population will be included in the interim futility analyses and final efficacy analysis.

- Cohort 3: African Patients >2 years and ≤ 5 years old
- Cohort 4: African Patients >6 months and ≤ 2 years old:
 - A targeted minimum of 10% of the total number of patients recruited in the lower NAI population ie, approximately 15 patients per treatment arm (if total numbers per arm are 150 for the efficacy analysis).

7.4.2 Age range step-down and FQ dose step-up procedures

Safety (up to Day 28 assessments) in the older age cohort will be assessed before proceeding down to the younger age range (see [Section 1.2](#) and [Section 8.4](#)).

Note: For DMC safety review, patients from both higher and lower NAI population will be considered. However, no predefined ratio between Africa and Asia patients are requested to move forward from one cohort of age to the next one. If requested by DMC, additional patients may be included and evaluated for safety.

1. For Cohort 1 (>14 years and <70 years and body weight ≥ 35 kg), a minimum of 10 patients per treatment arm receiving OZ439/FQ at 800/400 mg, 800/600 mg & 800/900 mg (Cohort 1a, ratio 1:1:1) will be assessed for safety up to Day 28.

The PK/QTc modeling results will estimate the QT effect of highest FQ plasma concentration before starting the Cohort 1b and may or may not be considered for decision rule. Within the Cohort 1b, the treatment arm OZ439/FQ at 800/1200 mg would be evaluated in a minimum of 10 patients versus 2 patients receiving OZ439/FQ at 800/900 mg (ratio 5:1) to maintain the study blinded. The two highest doses combinations will be assessed for safety up to Day 28 using Cohort 1b data for OZ439/FQ 800/1200 mg and pooled data from Cohorts 1a & 1b for OZ439/FQ 800/900 mg. The PK/QTc modeling results will estimate the QT effect of highest FQ plasma concentration before opening recruitment of the Cohort 2 and may or may not be considered for decision rule.

2. In the Cohort 2 (>5 and ≤ 14 years), a minimum of 5 patients/arm will be assessed for safety up to Day 28 (ratio 1:1:1 for Scenario A or 1:1:1:1 for Scenario B, see [Section 1.2](#), depending of the safety profile of OZ439/FQ 800/1200 mg) before opening recruitment in the Cohort 3.
3. In the Cohort 3 (>2 and ≤ 5 year), a minimum of 8 patients/treatment arm will be assessed for safety up to Day 28 before fully opening recruitment.
4. In the Cohort 4 (>6 month to ≤ 2 year), a minimum of 8 patients/treatment arm will be assessed for safety up to Day 28.

The safety evaluation will be performed by the DMC throughout the study with a frequency defined in the DMC charter.

8 STUDY TREATMENTS

8.1 INVESTIGATIONAL MEDICINAL PRODUCTS

The investigational medicinal products (IMPs) will be administered in the following order: FQ then OZ439.

All details regarding the preparation of IMPs, including suspension of FQ and OZ439, will be described in a separate pharmacy manual.

8.1.1 Ferroquine (FQ)

A combination of the following capsules will be used to compose the 4 doses; individual sachets containing sucrose granules are provided:

- 5 mg, 30 mg, 100 mg and 200 mg FQ or matching placebo.
- Placebo capsules are used to keep the same number of capsules in each weight band while keeping the FQ dose blinded. No patient will receive placebo only.
- For young children, capsules will be opened and their content will be diluted in water with sucrose granules in order to make it palatable and given as suspension.
- Oral route.
- Patients should have fasted from food and milk for 3 hours before administration. Neither food nor milk should be taken within 2 hour after the end of IMP dosing.
- Treatment duration: single dose at V2 Day 0.

8.1.2 Artefenomel (OZ439)

Individual sachets containing OZ439 (dose strengths from 150 mg to 800 mg + alpha tocopherol polyethylene glycol 1000 succinate [TPGS]) granules for oral suspension) and individual sachets containing sucrose granules.

- Oral route.
- The sucrose, adjusted to OZ439 dose, is added to the aqueous oral suspension prepared from OZ439 + TPGS granules for oral suspension in order to make it palatable.
- Patients should have fasted from food and milk for 3 hours before administration. Neither food nor milk should be taken within 2 hour after the end of IMP dosing.
- Once prepared, the suspension will have to be drunk within 2 hours and 20 minutes of the start of its preparation.
- The oral suspension should be drunk as quickly as possible and over a maximum of 30-minute period.
- Treatment duration: single dose at V2 Day 0.

8.1.3 Treatment arms

Individual patient treatment kit will be packed according to the weight band. The content of these kits are detailed below:

Table 3 - Treatment kits

Weight band	Compound	Treatment arm 1	Treatment arm 2	Treatment arm 3	Treatment arm 4
≥35 kg	FQ dosage (mg)	400	600	900	1200
	OZ439 dosage (mg)	800	800	800	800
	Sucrose for OZ oral suspension dosage (g)	15	15	15	15
≥24 and <35 kg	FQ dosage (mg)	300	450	675	900
	Sucrose for FQ oral suspension dosage (g)	2.813	2.813	2.813	2.813
	OZ439 dosage (mg)	600	600	600	600
	Sucrose for OZ oral suspension dosage (g)	11,25	11,25	11,25	11,25
≥15 and <24 kg	FQ dosage (mg)	200	300	450	600
	Sucrose for FQ oral suspension dosage (g)	2.813	2.813	2.813	2.813
	OZ439 dosage (mg)	400	400	400	400
	Sucrose for OZ oral suspension dosage (g)	7,5	7,5	7,5	7,5
≥10 and <15 kg	FQ dosage (mg)	150	225	335	450
	Sucrose for FQ oral suspension dosage (g)	2.813	2.813	2.813	2.813
	OZ439 dosage (mg)	300	300	300	300
	Sucrose for OZ oral suspension dosage (g)	5.625	5.625	5.625	5.625
≥7 and <10 kg	FQ dosage (mg)	100	150	225	300
	Sucrose for FQ oral suspension dosage (g)	2.813	2.813	2.813	2.813
	OZ439 dosage (mg)	200	200	200	200
	Sucrose for OZ oral suspension dosage (g)	3,75	3,75	3,75	3,75
≥5 and <7 kg	FQ dosage (mg)	75	115	170	225
	Sucrose for FQ oral suspension dosage (g)	2.813	2.813	2.813	2.813
	OZ439 dosage (mg)	150	150	150	150
	Sucrose for OZ oral suspension dosage (g)	2.813	2.813	2.813	2.813

FQ: ferroquine, OZ439: artefenomel, OZ: artefenomel

The appropriate volume of water needed for the preparation of each specific oral suspension will be mentioned in the Pharmacy Manual.

8.1.4 Re-dosing in the event of vomiting after OZ439 administration

- If a patient vomits within 5 minutes of the start of dosing with OZ439, they can be re-dosed with a freshly prepared new suspension from a new individual patient treatment kit assigned via IVRS/IWRS. No re-dosing of FQ will be performed.
- If vomiting occurs from 5 minutes to 35 minutes post start of OZ439, they should continue to take the OZ439 dose (if any left), but should not be re-dosed.
- If a patient vomits after 35 minutes from the start of OZ439 dosing, they should not be re-dosed.
- No re-dosing of FQ will be performed if a patient vomits during or after FQ administration but before OZ439 administration. In that case, OZ439 will not be administered and the patient will receive a rescue therapy as per [Section 8.9](#).

8.2 NONINVESTIGATIONAL MEDICINAL PRODUCT

Not applicable.

8.3 BLINDING PROCEDURES

8.3.1 Methods of blinding

For FQ, a double blind design has been set up. Therefore, in each weight band, each patient will receive the same number of capsules, see [Section 8.1.1](#).

Each treatment kit is labeled with a number, which is generated by a computer program from the Sponsor. Investigators do not have access to the randomization (treatment) code except under circumstances described in [Section 8.3.2](#).

- Consequently, the double blinded will be maintained.

For young children, FQ can be administered as an oral suspension (see [Section 8.1](#)). The oral suspension will be prepared by opening the capsules and mixing their content with sweetened water. Depending on the capsules strengths, the color of the content of capsules varies from white to orange. So the oral suspension will be prepared by an unblinded pharmacist. Once ready, there is no difference in color of the oral suspensions within each weight band which can then be administered to the patient by a caregiver (investigator or nurse) maintained blinded

- Study site procedures will be implemented to describe this process and ensure that only well identified and limited personnel will prepare FQ solution.

OZ439 is under open label design, but it will be included in the FQ treatment kit as described in [Section 8.5](#).

Refer to [Section 10.5](#) for suspected unexpected adverse drug reaction unblinding by the Sponsor.

8.3.2 Randomization code breaking during the study

Please see also [Section 8.3](#).

In case of an adverse event (AE), the code should only be broken in circumstances when knowledge of the IMP is required for treating the patient. If possible, a contact should be initiated with the Monitoring Team before breaking the code.

Code breaking can be performed at any time by using the proper module of the interactive voice response system (IVRS) and/or by calling any other phone number provided by the Sponsor for that purpose. If the blind is broken, the Investigator should document the date, time of day and reason for code breaking. As much as possible, patient will continue to be followed up to the End of Study according to study flow-chart (see [Table 1](#)).

The DMC will receive blinded by treatment group or unblinded (if necessary) confidential reports from an independent statistician for review, which have to be handled strictly confidentially. None of these reports can be delivered to unauthorized persons.

8.4 METHOD OF ASSIGNING PATIENTS TO TREATMENT GROUP

Centralized randomization and IVRS/IWRS related procedures will be detailed separately (IVRS/IWRS specifications manual).

- A total of 6 randomized treatment kit number lists will be generated centrally by Sanofi corresponding to the weight bands [> 35 kg, 24-35 kg, 15-24 kg, 10-15 kg, 7-10 kg and 5-7 kg].
- Patients will be randomized to one of the treatment arms via a centralized randomization system using an IVRS/IWRS. A patient will be considered randomized when the treatment number has been provided by the IVRS/IWRS, as documented from the IVRS/IWRS log file.
- At the screening visit, Visit 1, the site will contact the IVRS/IWRS to obtain a patient number for each patient for whom an informed consent has been obtained. Each patient will be allocated a patient number associated with the center and allocated in chronological order in each center.

IVRS will manage 3 patient randomization lists (one for Cohort 1a, a second for Cohort 1b and the third including all 4 cohorts) and allocates the treatment number and the corresponding treatment kit to the patient as follow:

- In Cohort 1a 30 patients will be randomized to one of the 3 treatment arms of OZ439/FQ. The randomization ratio is 1:1:1 (OZ439/FQ 800/400 mg: OZ439/FQ 800/600 mg: OZ439/FQ 800/900 mg).
- In Cohort 1b, if DMC has given the green light for proceeding with the 1200 mg dose of FQ, 12 patients will be randomized to one of the 2 treatment arms of OZ439/FQ. The randomization ratio is 1:5 (OZ439/FQ 800/900 mg: OZ439/FQ 800/1200 mg).
- After Cohorts 1a & 1b DMC review

- if DMC has given the green light for proceeding with the 1200 mg dose of FQ in younger patients according to the age step-down procedure, 155 patients (150 patients for the lower NAI population + 5 patients of Cohort 2 for the higher NAI population) will be randomized to one of the 4 treatment arms of OZ439/FQ according to the randomization ratio of 1:1:1:1 (treatment arm 1, treatment arm 2, treatment arm 3, treatment arm 4).
- if DMC does not give the green light for proceeding with the 1200 mg dose of FQ in younger patients according to the age step-down procedure, 155 patients (150 patients for the lower NAI population + 5 patients of Cohort 2 for the higher NAI population) will be randomized to one of the 3 treatment arms of OZ439/FQ according to the randomization ratio of 1:1:1 (treatment arm 1, treatment arm 2, treatment arm 3).
- The third randomization list will be stratified by region, and within Africa, age class (>14 years and <70 years/Asia; 5-14 years/Africa; 2-5 years/Africa; and 6 months-2 years/Africa). Details will be specified in the IVRS/IWRS specifications manual.
- A patient can be randomized only once.

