7 SELECTION OF PATIENTS

7.1 NUMBER OF PATIENTS

The study will be performed using interim assessments of futility. The number of African patients that will be required for the 'lower' naturally acquired immunity (NAI) per protocol population is 150 patients per treatment arm. However to allow for potentially higher variability, the target number of patients recruited will be 165 per treatment arm consisting of:

- 15 African patients per treatment arm greater than 5 years (ie, considered to have "higher" NAI) who will be evaluated within Cohort 1 & 2 and will not be included in the interim analyses for futility (*of note*, 17 patients should be included in treatment arm #3 since, in scenario B, 2 additional African patients would be added to Cohort 1b to maintain the blind); these patients will not be part of the per protocol efficacy population,
- Up to 150 patients per treatment arm from the 'lower' NAI population (ie, African patients ≤ 5 years old) who will be included in the interim analyses for futility.

Overall, this will give a total maximum number of 495 African patients (scenario A with 3 treatment arms) or 662 African patients (scenario B with 4 treatment arms) assuming no treatment arm is dropped 'early' for futility, ie, up to 165 African patients/treatment arm (except treatment arm #3 in which 167 patients should be included regarding scenario B) (see [Section 1.2](#), [Figure 1](#)). Twenty-one Asian patients will also be recruited.

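### Section 8.4 omits the words per treatment arm: it randomizes 155 patients over three or four arms, where the rest of the protocol needs 155 in each arm

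*Protocol*

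**What the plan says.** Section 8.4 describes three patient randomization lists.

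- First list: "In Cohort 1a 30 patients will be randomized to one of the 3 treatment arms of OZ439/FQ".
- Second list, if the 1200 mg dose goes ahead: "12 patients will be randomized to one of the 2 treatment arms of OZ439/FQ".
- Third list, after the DMC review of Cohorts 1a and 1b: "155 patients (150 patients for the lower NAI population + 5 patients of Cohort 2 for the higher NAI population) will be randomized". The sentence ends in one of two ways. With four arms the patients "will be randomized to one of the 4 treatment arms of OZ439/FQ according to the randomization ratio of 1:1:1:1"; with three arms they "will be randomized to one of the 3 treatment arms of OZ439/FQ according to the randomization ratio of 1:1:1".

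Other sections size the trial by arm. Section 7.1 says "the target number of patients recruited will be 165 per treatment arm", made up of 15 African patients older than 5 years and "Up to 150 patients per treatment arm from the 'lower' NAI population". It gives totals of 495 African patients for scenario A (three arms) and 662 for scenario B (four arms), with 21 Asian patients in addition. Section 7.4.1.1 sets Cohort 2 as "A minimum of 5 patients/arm (15 patients minimum if 3 treatment arms and 20 patients minimum if 4 treatment arms". Section 11.1 bases power on 150 evaluable patients per arm. Section 11.5 repeats 5 per arm for Cohort 2 and places the first futility look at 50 per arm.

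**The concern.** In Section 8.4 the figures 30 and 12 are totals over arms: 30 is 10 in each of three arms, and 12 is 10 plus 2. The 155 follows in the same sentence form with no qualifier, so within that section the natural reading is that it too is a total. That reading contradicts the patient counts in the rest of the protocol.

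The third list carries every patient in the efficacy analysis. If it were built to the literal number, neither the 150-per-arm final analysis nor its stated power could be reached. Section 8.4 leaves the list details to an IVRS/IWRS manual, so the sentence that the manual is to follow should not be open to two readings.

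**Working it through.** **Inputs**

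- Cohort 1a: 30 patients; Cohort 1b: 12 patients (Section 8.4).
- Lower-NAI patients: 150 per arm (Sections 7.1, 11.1 and 11.5).
- Cohort 2: 5 per arm (Sections 7.4.1.1 and 11.5).
- Stated totals: 495 and 662 African patients (Sections 7.1 and 11.1).
- Cohorts 1 and 2 together, scenario B: about 62 patients (Section 1.2).
- Success rule: lower limit of the two-sided exact 95% interval above 90% (Section 11.4.3.1). Assumed true rate: 96.4% (Section 11.1).

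**1. Reproduce the protocol's totals, taking 155 as per arm**

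- Scenario A: 30 + 3 × 155 = 30 + 465 = 495. Matches.
- Scenario B: 30 + 12 + 4 × 155 = 42 + 620 = 662. Matches.
- Cohorts 1 and 2 in scenario B: 42 + 4 × 5 = 62. Matches Section 1.2.

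**2. Take 155 as a total**

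| | Three arms | Four arms |
|---|---|---|
| Study total | 30 + 155 = 185 (stated 495) | 42 + 155 = 197 (stated 662) |
| Share of the list needed | 155/465 = 33.3% | 155/620 = 25.0% |
| Patients per arm on this list | 155/3 = 51.7 | 155/4 = 38.75 |
| Lower-NAI patients per arm | 150/3 = 50 | 150/4 = 37.5 |
| First futility look at 50 per arm | just reached, if all 50 are evaluable | not reached |

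On this reading Cohort 2 would have 5 patients in all, against the 15 or 20 in Section 7.4.1.1.

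**3. Power under each reading (exact binomial, true rate 96.4%)**

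- 150 per arm: at least 143 successes are needed. Power is 82.5% without futility looks and 81.7% with the Beta(9.5, 0.5) rule at 50, 75, 100 and 125. This agrees with the stated figure of at least 80%.
- 50 per arm: all 50 must succeed; power 0.964^50 = 16.0%.
- 37 or 38 per arm: all must succeed; power 0.964^37 = 25.8% or 0.964^38 = 24.8%.

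**4. Scenario A reached after Cohort 1b**

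Section 1.2 also counts as scenario A the case in which arm 4 is stopped after the review at the end of Cohort 1b. The 12 Cohort 1b patients are then already enrolled: 30 + 12 + 465 = 507. By arm: 165 + 165 + 167 + 10 = 507. Section 7.1 gives 495 as the maximum for scenario A.

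**The case against.** The strongest reply is that this is an editorial slip. The bracket in Section 8.4 names the two components, both appear per arm elsewhere, and a reader who adds up the totals recovers the intent. Recruitment is governed by futility or by 150 evaluable patients per arm (Section 11.1), not by Section 8.4, and the IVRS/IWRS manual may already hold the right number. This stands as an account of the cause and limits the likely harm. It does not remove the contradiction in the section that instructs the randomization.

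Three stronger readings are tempting, and the documents do not support them.

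- *The trial is under-sized.* A reader might infer this from the shares of a third and a quarter. The sizing in Sections 7.1 and 11.1 is per arm, and its totals and power reproduce.
- *On the literal reading every arm falls short of the first futility look.* With three arms the literal number gives 50 lower-NAI patients per arm, which is that look. Only the four-arm case falls short.
- *Section 8.4 is wrong because it omits 507.* It states no study total. The figure affected is the 495 in Section 7.1, repeated as approximate in Section 11.1 and the synopsis.

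A correction giving 465 or 620 must also say that these are African patients. Section 8.4 gives the third list an Asian stratum, and Section 7.1 counts the 21 Asian patients separately.

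**Conclusion.** The point holds as a wrong figure in Section 8.4. The cause is almost certainly an omitted *per treatment arm*, because 155 per arm reproduces 495 and 662 exactly and 155 in total does not. Taken literally, the list is short by 310 of 465 patients with three arms and by 465 of 620 with four.

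The power figures of 16% to 26% describe only what would follow if the list were built to the literal number. They are not a statement about the planned design, whose power of at least 80% is confirmed. They assume that all lower-NAI patients are evaluable and split evenly over the arms. Whether the IVRS/IWRS specification carries the slip cannot be seen from the protocol.

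The difference between 507 and 495 is a separate, smaller matter: 12 patients, in one branch of scenario A only.

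**What to change.** - **Section 8.4, four-arm bullet:** write 155 African patients per treatment arm (620 in total).
- **Section 8.4, three-arm bullet:** write 155 African patients per treatment arm (465 in total).
- **Both bullets:** keep the split of 150 lower-NAI plus 5 Cohort 2 patients, and state that Asian patients are additional.
- **IVRS/IWRS specification:** confirm that the third list uses the per-arm number.
- **Section 7.1, and the matching figure in Section 11.1 and the synopsis:** add that the African total is 507 if scenario A is reached after Cohort 1b.

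The cost is a few words in the protocol and one check of the specification. The Section 8.4 correction adds no patients to the plan. The 507 note only counts patients who would already be enrolled in that branch.
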